## **7.0 Statistical Considerations**

This is a pilot randomized controlled trial comparing the support group using active video game-based physical activity intervention to the existing UTMB breast cancer support group

with pedometer. We will measure feasibility and acceptability-related process measures and outcome measures. MD Anderson personnel ([name]) will lead the cohorts 1-4 data analyses and manuscript development. Data provided to MD Anderson personnel for data analyses will be de-identified.

**Aim 1: Evaluate the feasibility and acceptability of active video game-based physical activity intervention among BC survivors within the support group setting.** Feasibility findings will be based on descriptive analyses. We will compare our summary results to other studies. Examples of feasibility findings include: number of completed home-based worksheets, number of participant attendance on a weekly basis, number of participants who completed the program and the program activities, and weekly step goal achieved. Adherence is considered as a feasibility outcome. Weekly adherence is defined as the participant wearing Wii Fit meter for  $\geq 5$  days and attend at least 10 group sessions.

**Aim 2: Compare the support group using the active video game-based physical activity intervention (intervention group) to the existing UTMB breast cancer support group with pedometer (control group for cohorts 1-3) or the telephone-based support group with the UTMB support group (control group for cohort 4).** We will use analysis of covariance (ANCOVA) to test the post-intervention differences at 12-weeks (physical activity) between the two groups, controlling for baseline and other covariates that are significantly different at baseline. Intent to treat analysis will be used to handle missing data. ANCOVA will also be used to evaluate the secondary outcomes (physical function and quality of life). We will explore the changes in psychosocial variables using linear mixed models to investigate differences between groups and over here time points. Since this is a pilot study and it is not powered to detect significant differences of small to moderate effects, we hypothesized that the intervention group will show an improvement in physical activity, physical function, and quality of life compared to the control group. We also hypothesize that the intervention group will show an improvement in self-reported scores on self-efficacy, self-regulation, intrinsic motivation

**Aim 3: Develop tools for implementation of the Pink Warrior intervention within the clinic and community settings.** Development of a trainer's manual for the intervention will mainly be based on descriptive analyses using the facilitator's weekly group log. The facilitators will indicate whether or not they were able to cover the entire session as planned and facilitator will also be asked to provide feedback regarding the facilitator's guide and their feedback regarding the group activities.

7.1 Sample Size Calculation. The primary purpose of this study is to evaluate the feasibility of intervention components and study procedures to inform a larger intervention trial. This is a necessary research that is related to research focused on cancer survivors. For these reasons, a sample size of 60 is deemed appropriate to test intervention. A sample size of 60 is enough to detect an increase in 1000 to 2000 steps from baseline to follow-up based on other published pedometer-based interventions. We will use our findings from this pilot study to establish effect sizes and inform the power and sample size estimates for larger trials. In the fourth cohort, a sample size of 20 is deemed appropriate to determine the Cohen's d effect sizes the intervention has on activity level (average number of steps/day), physical function, and self-reported quality of life.

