### 4. Research Design and Methods

This study will evaluate the feasibility and acceptability of active video game-based physical

activity intervention among BC survivors within the support group setting. In addition, we will also compare the changes in physical activity among participants who were in the active video game-based physical activity intervention support group to those who were in the existing the UTMB breast cancer support group. Participants (N=60) will be randomized to participate in the support group that uses the active video game-based physical activity intervention (intervention group) or in the existing UTMB breast cancer support group with pedometers (control group) for 12 weeks. The home-based self-paced portion of the intervention will mainly be delivered through the participant manual. In the fourth cohort, BC survivors (N=20, aged 55 to 79 due to the aging grant restrictions) will be recruited and randomly assigned to intervention or control condition for a 12-week period. The intervention group will participate in weekly active video game web-based group sessions. The control group will receive weekly conference calls plus wearable tracker to track their physical activity for 12 weeks.

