By wearing the Fitbit, participants will be able to track individual and group daily steps on the Fitbit dashboard. Having the ability to see the weekly accomplishments will further enhance motivation for activity through social comparison and relatedness.

4.5 Control group procedure. Participants in cohort 1-3 that are randomized to the control group will be introduced to the current facilitator for the existing Breast Cancer Support Group at the UTMB Breast Health and Imaging Center after the initial assessment. Control group participant will be encouraged to participate in the Breast Cancer Support Group for the next 12-weeks on a monthly basis. Examples of topics covered in the Breast Cancer Support Group are presented in **Appendix D**. The support group follows the *Navigating Life’s road Map After Breast Cancer* curriculum from the Reconstruction of a Survivor (<http://www.reconstructasurvivor.org/index.html>) organization. Control group participant will also be provided a pedometer (Digi Walker or Omron Tri Axis HJ-

Figure 3. Digi-Walker or Omron Tri Axis HJ-321 Pedometer

321) to be worn for 12-weeks (Figure 3). Participants will have a choice to use either a Digi Walker or Omron Tri Axis pedometer. Participants in the control group will also receive the American Cancer Society's personal health manager kit as it is standard of practice at the UTMB Breast Health and Imaging Center. They will also be recording their activities on a daily, weekly, and monthly basis.

For the fourth cohort, weekly conference calls to check on participants' well-being and to provide survivorship information will be scheduled over the 13-week study period (Appendix B2d). Control group participants in the cohort 4 will be given a wearable tracker with charger to use during the study period. A list of local breast cancer/cancer support groups will also be given to the participants that is available on the UTMB website. MD Anderson personnel (e.g., [name]) will be involved in cohort 4 control group activities.

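### The Aim 2 ANCOVA has no cohort term and does not say whether cohort 4, which has a different comparator, is analysed with cohorts 1-3 or apart from them

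*Combined protocol and SAP*

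**What the plan says.** Section 7.0, Aim 2, names one intervention group and two controls: the existing support group with pedometer as "control group for cohorts 1-3) or the telephone-based support group with the UTMB support group (control group for cohort 4". The model follows: "We will use analysis of covariance (ANCOVA) to test the post-intervention differences at 12-weeks (physical activity) between the two groups". The rule for adjustment in that model is stated as "controlling for baseline and other covariates that are significantly different at baseline". No cohort term, stratification, arm-by-cohort term or separate cohort 4 model is mentioned.

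On scope, the opening of section 7.0 says that the analysis personnel "will lead the cohorts 1-4 data analyses and manuscript development". The same paragraph describes the trial only as a comparison with the pedometer support group.

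Section 7.1 treats the cohorts apart. For cohorts 1-3: "A sample size of 60 is enough to detect an increase in 1000 to 2000 steps from baseline to follow-up". For cohort 4: "In the fourth cohort, a sample size of 20 is deemed appropriate to determine the Cohen's d effect sizes", covering steps per day, physical function and quality of life.

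The two control conditions are set out elsewhere. Section 4.5, for cohorts 1-3: "Control group participant will be encouraged to participate in the Breast Cancer Support Group for the next 12-weeks on a monthly basis", with a pedometer. Section 4, for cohort 4: "The control group will receive weekly conference calls plus wearable tracker to track their physical activity for 12 weeks".

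**The concern.** The comparison in cohort 4 differs from the one in cohorts 1-3 in ways that could change the effect on physical activity:

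- **Control contact:** a monthly group in cohorts 1-3, weekly calls in cohort 4 (sections 4 and 4.5).
- **Device:** Wii Fit meter against pedometer in cohorts 1-3, a wearable tracker in both arms of cohort 4 (Table 1). Section 2 argues that trackers give fuller feedback than pedometers, so on the protocol's own reasoning the device is part of the contrast in cohorts 1-3 and largely cancels in cohort 4.
- **Delivery and content:** in person against web-based, with grip exercise added in cohort 4 (section 4.4).
- **Age:** 18 or older against 55 to 79 (section 4.3, inclusion criteria).

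If cohort 4 goes into the same model, the result averages over two contrasts. Section 7.1 intends the pilot's effect sizes to inform the power of larger trials, and a trial with one delivery mode and one comparator would need the estimate for that contrast. Because section 7.0 is silent, the choice between pooling and separating could also be made after the data are seen.

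**Working it through.** **1. The plan's own figures.** Section 4.2 gives the planned allocation as 5:5, 5:5, 20:20 and 10:10. The counts agree: 10 + 10 + 40 = 60, and 60 + 20 = 80. The 60 cannot be reproduced as a power calculation, because alpha, power and SD are not given. If a two-sided 0.05 test and 80% power are assumed, 30 per arm suffices for a between-arm difference only when SD ≤ difference / ((1.96 + 0.84) × √(2/30)). That is about 1,382 steps for a difference of 1,000, or 2,765 for 2,000. No calculation is offered for an analysis of 80.

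**2. What a literal all-cohort model would estimate.** Assume equal SD and the planned allocation.
- Variance of the arm difference, in SD² units: cohorts 1-3, 2/30 = 0.067; cohort 4, 2/10 = 0.200.
- Weight on cohorts 1-3: 15 / (15 + 5) = 0.75. Weight on cohort 4: 0.25.
- Pooled effect = 0.75 × (effect in cohorts 1-3) + 0.25 × (effect in cohort 4).

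With assumed true effects of 1,000 and 0 steps/day, the pooled value is 750. With 1,000 and 2,000 it is 1,250. It equals both cohort effects only if they are the same.

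**3. Whether the covariate rule brings cohort in.** A covariate beyond the baseline value enters only if it differs significantly between arms.
- If the planned 1:1 split is achieved in every cohort, cohort is exactly balanced, any test of imbalance is zero, and cohort cannot qualify.
- If it is not achieved (the randomization section describes a random number generator and sealed envelopes, but no blocking or stratification by cohort), any imbalance short of significance stays unadjusted.

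**4. Whether cohort matters within cohorts 1-3.** The activity monitor changes from the wGT3X in cohorts 1-2 to the GT9X from cohort 3 (section 4.6, Table 3a), and group sessions were shortened from 90 to 60 minutes after cohort 2 (section 4.4). Both are reasons for a cohort term there too.

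**5. Cost of separating.** Unadjusted 95% half-width of the standardised difference = 1.96 × √(2/n per arm):

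| Analysis | n per arm | Half-width (SD) |
|---|---|---|
| All cohorts | 40 | 0.44 |
| Cohorts 1-3 | 30 | 0.51 |
| Cohort 4 | 10 | 0.88 (0.94 with t, 18 df) |

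The main interval widens by a factor of √(40/30) = 1.15. Three cohorts cost 2 df: 60 − (intercept 1 + arm 1 + baseline 1 + cohort 2) = 55 residual df, against 57 without cohort.

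**6. An arm-by-(cohort 4 vs 1-3) term.** SE = √(0.067 + 0.200) = 0.516 SD. For a true difference of 0.8 SD, 0.8/0.516 − 1.96 = −0.41, which gives power of about 34% at two-sided 0.05. For 0.5 and 1.0 SD the power is about 16% and 49%. The all-cohort model with this term uses 3 + 1 = 4 df.

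**The case against.** The strongest reply is that pooling is nowhere stated. Aim 2 labels two control groups, so the ANCOVA sentence can be read as intervention against each cohort's own control. The mention of cohorts 1-4 in section 7.0 says who does the work and uses the plural. Section 7.1 already treats cohort 4 as a separate estimate. This stands: a reader might infer that the plan pools all 80, but the documents do not establish it. What remains is that section 7.0 is silent where section 7.1 points towards separation, and that the one model written down has no cohort term.

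A reader might also infer that a pooled estimate would answer neither comparison. That goes too far. With 1:1 allocation in every cohort, it is a valid weighted average effect of the game-based programme against control, dominated by cohorts 1-3.

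Three further points have force. Cohort 4 keeps the same curriculum (section 4.4), and its age range lies inside that of cohorts 1-3. Adjustment for baseline should absorb part of any between-cohort difference in activity, so the precision lost by omitting cohort cannot be sized from the documents. If arms are balanced within cohort, the omission costs precision and causes no systematic bias. Finally, this is a feasibility pilot that disclaims power for small to moderate effects, which limits how serious the point can be.

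**Conclusion.** The point holds as a gap in specification. The plan joins two different comparators under one ANCOVA, does not say whether cohort 4 is included, and has a covariate rule that cannot be relied on to bring cohort in. A literal all-cohort run would give a 75/25 average that is valid but hard to carry into the design of a later trial. The weights assume equal SD, the planned allocation and no dropout. The step effects of 1,000, 2,000 and 0 are illustrations, not estimates. The half-widths are unadjusted, and the interaction power assumes a two-sided alpha of 0.05. The silence about cohort follows from the text alone and depends on none of these assumptions.

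**What to change.** In section 7.0:

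- Pre-specify cohort as a fixed factor in the Aim 2 ANCOVA, whatever the baseline tests show.
- Make cohorts 1-3 (n=60) the main comparison, adjusted for the baseline value and cohort (2 df).
- Report cohort 4 (n=20) separately as an effect estimate with a confidence interval, in line with section 7.1.
- Keep any all-cohort model secondary, with cohort and an arm-by-(cohort 4 vs 1-3) term (4 df). Treat that term as descriptive because of its low power, and describe the overall result as an average over two contrasts.

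The cost is a few sentences and one extra model. The price in precision is a main half-width of about 0.51 SD instead of 0.44 SD, and a cohort 4 interval that is wide however it is computed (0.88 to 0.94 SD). The cohort term alone is close to free. It does not settle how physical function is combined when its instruments change after cohort 2 (section 4.6); that needs its own rule.

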Each week will consist of both structured group sessions and self-paced home-based sessions. The weekly structured group session will last approximately 90 minutes. Weekly worksheets and participant manual will be provided to promote home-based physical activities. The participant manual will consist of detailed information of the weekly topic to be reviewed within the group setting. Participant manual will be used for self-paced home-based materials. Each of the weekly sessions will consist of three components: 1) a *cognitive-behavioral skill building* component to promote the increase and maintenance of physical activity behavior, 2) an *activity demonstration and practice* component to provide guided practice and to increase mastery of activity skills, and 3) a *cancer survivorship discussion* component to provide support and resources for BC survivors. Participant manual is available for review in **Appendix B**.

Based on participant feedback we received from the first and second cohorts, we are changing the length of group sessions to 60 minutes and adding an additional healthy eating discussion topic. We will also provide cancer survivorship discussion summary sheet per participants’ suggestions. Updated participant manual is available in Appendix B1. MD Anderson personnel (e.g., [name]) will be involved in cohort 4 intervention delivery activities.

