Within the *cognitive-behavioral skill building component*, the adapted *Pink Warrior* intervention content will focus on helping BC survivors overcome barriers to becoming active and to increase self-regulation skills. The behavior change strategies include: getting feedback regarding physical activity, self-monitoring, goal-setting, action planning, gaining knowledge regarding benefits of physical activity, and evaluation of value toward activity. We specifically chose these behavior change strategies because recent meta-analysis, which provided a comprehensive review of published physical activity programs, have shown effectiveness of these strategies in increasing physical activity. The behavioral change strategies will address activity barriers such as: lack of self-efficacy related to physical activity, lack of time due to competing demands, and lack of motivation due to general reasons or fatigue.

Active video games that involve motion-controlled movement will be used for the *activity demonstration and practice component* of the *Pink Warrior* intervention for two reasons. First, they are a cost-effective way to deliver a physical activity program in the community setting without the need to hire an exercise trainer. Second, research has shown active games are a unique and effective platform for increasing physical activity and motivation. By design, active video games will produce enjoyment, increase self-efficacy, and increase motivation to increase physical activity through delivering evidence-based behavior strategies such as modeling, guided practice, providing instantaneous feedback, providing various activity options, and increases opportunity for survivors to relate to one another through social play. Furthermore, by wearing the Wii Fit fitness tracker in cohort 1-3 (Figure 2), participants will be able to track individual and group’s daily steps. They will also be recording their activities on a daily, weekly, and monthly basis. Having the ability to see the weekly accomplishments will further enhance motivation for activity through social comparison and relatedness.

Figure 2. Wii Fit Meter and Group Results

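### The Aim 2 ANCOVA has no allowance for weekly group delivery; if outcomes correlate within session groups, its intervals will be too narrow by an amount the plan should show

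*Combined protocol and SAP*

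**What the plan says.** The between-group analysis is in section 7.0, Aim 2: "We will use analysis of covariance (ANCOVA) to test the post-intervention differences at 12-weeks (physical activity) between the two groups". The adjustment terms are given only in general form: the model is described as "controlling for baseline and other covariates that are significantly different at baseline". ANCOVA is also named for physical function and quality of life. No term for session group, facilitator or cohort is listed, and no cluster-robust variance. The only mixed models are for the psychosocial variables, "linear mixed models to investigate differences between groups and over here time points", and no group random effect is described for them. Section 7.1 contains no design effect.

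The intervention is delivered in groups in every cohort. Section 4.4 states: "Each week will consist of both structured group sessions and self-paced home-based sessions". For cohort 4, section 4 states: "The intervention group will participate in weekly active video game web-based group sessions". Section 4.4 says that game play "increases opportunity for survivors to relate to one another through social play", and that participants can follow both their own and the group's daily steps. Table 1 lists other participants as role models and as a source of feedback.

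Controls also have a shared setting, of a looser kind. In cohorts 1-3, section 4.5 says: "Control group participant will be encouraged to participate in the Breast Cancer Support Group for the next 12-weeks on a monthly basis". In cohort 4 they receive weekly conference calls.

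Under the randomisation procedures in section 4.3, each study ID is assigned individually.

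**The concern.** This is an individually randomised trial with group delivery. ANCOVA estimates its error variance as if each participant's residual were independent of the others. The intervention is built to weaken that independence: members play together, see one another's progress and are expected to be motivated by it. Steps per day are both what the group watches and an outcome, so the mechanism acts directly on the endpoint.

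With positive within-group correlation, 40 intervention participants carry less information than 40 independent ones. Confidence intervals for physical activity, physical function and quality of life would be too narrow, and a nominal test would reject too often. The pilot's effect sizes are meant to inform a larger trial of the same group-delivered programme, and nothing in section 7.1 warns its designers to allow for clustering.

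**Working it through.** **The plan's own figure.** Section 7.1 says 60 participants are enough to detect 1000 to 2000 steps. This cannot be reproduced, because no SD, power or significance level is given. At an assumed two-sided 5% level, 80% power and 30 per arm, the required SD is difference / ((1.960 + 0.842) × √(2/30)) = difference / 0.7234. That is 1382 for 1000 steps and 2765 for 2000. No clustering allowance is visible in the statement, and none can be inferred.

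**Inputs from the documents.** Intervention-arm sizes by cohort are 5, 5, 20 and 10 (section 4.2), and the control arm is the same.

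**Assumptions.** ICC 0.01, 0.05 and 0.10; two-sided 5% level; all four cohorts analysed together; session-group sizes as shown below.

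**Formulas.**
- Effective group size: m_eff = Σm² / Σm.
- Design effect: DE = 1 + ICC × (m_eff − 1).
- Ratio r of true SE to independence SE: √((DE + 1)/2) if only the intervention arm is clustered, and √DE if both arms are clustered alike (equal arms).
- Actual type I error: 2 × (1 − Φ(1.96 / r)).

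**One intervention group per cohort.** m_eff = (25 + 25 + 400 + 100)/40 = 550/40 = 13.75. DE = 1.13, 1.64 and 2.28 at the three ICCs. Worked at ICC 0.05: DE = 1 + 0.05 × 12.75 = 1.6375; r = √(2.6375/2) = 1.148; 1.96/1.148 = 1.707; type I error 8.8%.

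**Cohort 3 as two groups of 10.** m_eff = (25 + 25 + 100 + 100 + 100)/40 = 350/40 = 8.75.

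**All groups of 5.** m_eff = 5.

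| Scenario | SE ratio at ICC 0.01 / 0.05 / 0.10 | Type I error |
|---|---|---|
| Intervention arm only, groups 5, 5, 20, 10 | 1.03 / 1.15 / 1.28 | 5.7% / 8.8% / 12.6% |
| Intervention arm only, cohort 3 as 10 + 10 | 1.02 / 1.09 / 1.18 | 5.4% / 7.3% / 9.6% |
| Intervention arm only, all groups of 5 | 1.01 / 1.05 / 1.10 | 5.2% / 6.2% / 7.4% |
| Both arms at the same ICC, groups 5, 5, 20, 10 | 1.06 / 1.28 / 1.51 | 6.5% / 12.6% / 19.4% |

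**Check by simulation.** The planned ANCOVA was simulated with a group random effect and no treatment effect (10,000 runs per setting, groups 5, 5, 20, 10). Type I error was 5.6%, 8.6% and 12.7% with the intervention arm clustered, and 6.4%, 12.4% and 19.0% with both arms clustered. At ICC 0 the test kept its level (5.1% and 5.0%). A cohort term alone is not a cure: at ICC 0.05 in both arms, with a shared cohort variance of 0.10, the rate was 13.3% with the term and 11.8% without it.

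**The case against.** The strongest reply is that individual randomisation protects the test. If neither assignment nor group membership changes anyone's outcome, the ANCOVA keeps its level. The inflation arises only if groups shift their members' outcomes and are regarded as a sample from the groups that might have been run. That is correct, so the point has to be conditional. It does not remove the point, because the protocol's own theory is that groups do shift outcomes, and the results are meant for a programme that other groups will use.

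Three further objections stand in part:
- **Group size.** Section 4.2 gives arm sizes, not session-group sizes. Treating cohort 3 as one group of 20 supplies 400 of the 550 in Σm². Two sites are named in the eligibility criteria, so smaller groups are quite possible. The smaller figures therefore belong beside the larger ones.
- **Controls.** In cohorts 1-3 they are only encouraged to attend, monthly. Giving them the same ICC as weekly interactive play, in separate cohort-sized clusters, is an upper bound and not an expectation.
- **Purpose.** Feasibility is primary, section 7.0 says the trial is not powered for small to moderate effects, and no decision rule depends on the p-value.

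A reader might also infer that understated standard errors pass straight into the next trial's sample size. The documents do not say that: section 7.1 carries forward effect sizes. The narrower point is that those effect sizes would be reported with too much apparent precision and with no reminder to allow for group delivery.

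**Conclusion.** The gap is real and the consequence is conditional. The Aim 2 ANCOVA makes no allowance for within-group correlation, and no other section supplies one. If such correlation exists, standard errors are too small. With clustering in the intervention arm only, a nominal two-sided 5% test runs at about 5.2% to 12.6% over the assumed ICCs and group sizes. With equal clustering in controls and one group per arm per cohort, the upper-bound figures are 6.5% to 19.4%.

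A reader might go further and say that the standard errors are wrong and that the trial's 5% test is not a 5% test. The documents do not support that as fact: they state no significance level, no ICC and no number of session groups, and at ICC 0.01 with groups of 5 the excess is negligible. This is best treated as a cheap improvement to the plan, and the feasibility purpose limits its severity.

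**What to change.** In section 7.0:
- Keep the ANCOVA as the main estimate, and state that its interval assumes no correlation within session groups.
- Record each participant's session group, and report the number and size of groups by cohort and arm.
- Pre-specify a sensitivity interval at ICC 0.01, 0.05 and 0.10. Multiply the SE by √((DE + 1)/2) for clustering in the intervention arm only, and by √DE for clustering in both arms. Take DE = 1 + ICC × (Σm²/Σm − 1) from the actual group sizes.

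In section 7.1, state that sample size estimates for the larger trial will include a design effect for group delivery.

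A random session-group effect is the usual alternative, but three or four groups per arm leave only about 4 to 6 between-group degrees of freedom, and its variance would be poorly estimated. The sensitivity interval avoids this because the ICC is assumed.

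The cost is a few lines of analysis and one item of record-keeping. With one intervention group per cohort, sensitivity intervals would be about 3% to 28% wider with the intervention arm clustered, and up to about 50% wider if both arms cluster at ICC 0.10.
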